# Table 14.3.1.5.1.3: Shift Summary of Overall Electrocardiogram (ECG) Assessments (Safety Population) (Page 2 of 2)

Overall ECG Assessment (per Investigator)		Placebo (N=xxx)			Serlopitant 5 mg (N=xxx)	
Baseline	Normal	Latest Follow-up Abnormal, NCS	Abnormal, CS	Normal	Latest Follow-up Abnormal, NCS	Abnormal, CS
Normal Normal	XX ( XX.X%)	$\frac{\text{Abhormal, NCS}}{\text{xx} (\text{xx.x\%})}$	xx ( xx.x%)	xx ( xx.x%)	xx ( xx.x%)	xx ( xx.x%)
Abnormal, NCS	xx ( xx.x%)	xx ( xx.x%)	xx ( xx.x%)	xx ( xx.x%)	xx ( xx.x%)	xx ( xx.x%)
Abnormal, CS	xx ( xx.x%)	xx ( xx.x%)	xx ( xx.x%)	xx ( xx.x%)	xx ( xx.x%)	xx ( xx.x%)

Note: No imputation of missing values. Baseline is the latest recorded value prior to first dose of study drug. "Latest Follow-up" visit includes the latest available follow-up information for each subject from the 3-Week or 5-Week Follow-up visits.

NCS=Not Clinically Significant; CS=Clinically Significant.

SOURCE: USERNAME\SPONSOR\PROJECT\JOBNAME (DATE,TIME)

Table 14.3.1.5.2.1: Summary of Post-Drug Electrocardiogram (ECG) Parameter Abnormalities (Safety Population Consenting to Protocol Version 3.0) (Page 1 of 2)

	Placebo (N=xxx)	Serlopitant 5 mg (N=xxx)
Number of Subjects with Post-Drug ECG Results	XXX	XXX
PR Interval		
> 200 msec	xx ( xx.x%)	xx (xx.x%)
> 220 msec	xx ( xx.x%)	xx ( xx.x%)
Change from On-Drug Baseline in PR Interval		
>= 25% and > 200 msec	xx ( xx.x%)	xx ( xx.x%)
QRS Interval		
> 110 msec	xx (xx.x%)	xx ( xx.x%)
> 120 msec	xx ( xx.x%)	xx ( xx.x%)
Change from On-Drug Baseline in QRS Interval		
>= 25% and $> 110$ msec	xx (xx.x%)	xx ( xx.x%)
>= 25% and > 120 msec	xx ( xx.x%)	xx ( xx.x%)
QTcF Interval		
> 450 - 470 msec	xx (xx.x%)	xx ( xx.x%)
> 470 - 500 msec	xx (xx.x%)	xx ( xx.x%)
> 500 msec	xx ( xx.x%)	xx ( xx.x%)
Change from On-Drug Baseline in QTcF Interval		
> 30 - 60 msec	xx ( xx.x%)	xx (xx.x%)
> 60 msec	xx ( xx.x%)	xx ( xx.x%)
QTcF Interval > 500 msec and Change from On-Drug Baseline > 60 msec	xx ( xx.x%)	xx ( xx.x%)

Note: No imputation of missing values. On-Drug Baseline is the latest recorded value prior to last dose of study drug. Change calculated as post-baseline – baseline.

SOURCE: USERNAME\SPONSOR\PROJECT\JOBNAME (DATE,TIME)

Table 14.3.1.5.2.1: Summary of Post-Drug Electrocardiogram (ECG) Abnormalities (Safety Population Consenting to Protocol Version 3.0) (Page 2 of 2)

Number of Subjects with Post-Drug ECG Results	Placebo (N=xxx) xxx	Serlopitant 5 mg (N=xxx) xxx
QTcB Interval		
> 450 - 470 msec	xx ( xx.x%)	xx ( xx.x%)
> 470 - 500 msec	xx ( xx.x%)	xx ( xx.x%)
> 500 msec	xx ( xx.x%)	xx ( xx.x%)
Change from On-Drug Baseline in QTcB Interval		
> 30 - 60 msec	xx ( xx.x%)	xx ( xx.x%)
> 60 msec	xx ( xx.x%)	xx ( xx.x%)
QTcB Interval > 500 msec and Change from On-Drug Baseline > 60 msec	xx ( xx.x%)	xx ( xx.x%)

Note: No imputation of missing values. On-Drug Baseline is the latest recorded value prior to last dose of study drug. Change calculated as post-baseline – baseline.

SOURCE: USERNAME\SPONSOR\PROJECT\JOBNAME (DATE,TIME)

Table 14.3.1.5.2.2: Summary of Post-Drug Electrocardiogram Parameters (Safety Population Consenting to Protocol Version 3.0) (Page 1 of xx)

	Placebo	Serlopitant 5 mg
	(N=xxx)	(N=xxx)
<parameter> (<units>)</units></parameter>		
On-Drug Baseline		
n	XX	XX
Mean	XX.X	XX.X
SD	XX.XX	XX.XX
Median	XX.X	XX.X
Min. to Max.	xx to xx	xx to xx
5-Week Follow-up		
n	XX	XX
Mean	XX.X	XX.X
SD	XX.XX	XX.XX
Median	XX.X	XX.X
Min. to Max.	xx to xx	xx to xx
Absolute Change from On-Drug Baseline		
n	XX	XX
Mean	XX.X	XX.X
SD	XX.XX	XX.XX
Median	XX.X	XX.X
Min. to Max.	xx to xx	xx to xx

Note: No imputation of missing values. On-Drug Baseline is the latest recorded value prior to last dose of study drug. Change calculated as post-baseline – baseline.

SOURCE: USERNAME\SPONSOR\PROJECT\JOBNAME (DATE,TIME)

Table to include parameters "ECG Mean Heart Rate (beats/min)", "PR Interval, Aggregate (msec)", "QRS Duration, Aggregate (msec)", "QT Interval, Aggregate (msec)", "QTcB Interval, Aggregate (msec)", "RR Interval, Aggregate (msec)".

Table 14.3.1.5.2.3: Shift Summary of Post-Drug Overall Electrocardiogram (ECG) Assessments (Safety Population Consenting to Protocol Version 3.0)

Overall ECG Assessment (per Investigator)	Placebo (N=xxx)			Serlopitant 5 mg (N=xxx)		
	5	S-Week Follow-up		5	-Week Follow-up	
On-Drug Baseline	Normal	Abnormal, NCS	Abnormal, CS	Normal	Abnormal, NCS	Abnormal, CS
Normal	xx ( xx.x%)	xx ( xx.x%)	xx ( xx.x%)	xx ( xx.x%)	xx ( xx.x%)	xx ( xx.x%)
Abnormal, NCS	xx ( xx.x%)	xx ( xx.x%)	xx ( xx.x%)	xx ( xx.x%)	xx ( xx.x%)	xx ( xx.x%)
Abnormal, CS	xx ( xx.x%)	xx ( xx.x%)	xx ( xx.x%)	xx ( xx.x%)	xx ( xx.x%)	xx ( xx.x%)

Note: No imputation of missing values. On-Drug Baseline is the latest recorded value prior to last dose of study drug.

NCS=Not Clinically Significant; CS=Clinically Significant.
SOURCE: USERNAME\SPONSOR\PROJECT\JOBNAME (DATE,TIME)

Table 14.3.1.6.1: Summary of Vital Signs (Safety Population)
(Page 1 of xx)

	Placebo	Serlopitant 5 mg
	(N=xxx)	(N=xxx)
<parameter> (<units>)</units></parameter>		
Baseline		
n	XX	XX
Mean	XX.X	XX.X
SD	XX.XX	XX.XX
Median	XX.X	XX.X
Min. to Max.	xx to xx	xx to xx
Week 2		
n	XX	XX
Mean	XX.X	XX.X
SD	XX.XX	XX.XX
Median	XX.X	XX.X
Min. to Max.	xx to xx	xx to xx
Absolute Change from Baseline		
n	XX	XX
Mean	XX.X	XX.X
SD	XX.XX	XX.XX
Median	XX.X	XX.X
Min. to Max.	xx to xx	xx to xx

Note: Baseline is the latest recorded value prior to first dose of study drug. Change calculated as post-baseline – baseline. "Latest Follow-up" visit includes the latest available follow-up information for each subject from the 3-Week, 4-Week or 5-Week Follow-up visits.

SOURCE: USERNAME\SPONSOR\PROJECT\JOBNAME (DATE,TIME)

Table to include parameters in following order: "Temperature (degrees Celsius)", "Respiration Rate (breaths/min)", "Heart Rate (beats/min)", "Systolic Blood Pressure (mmHg)", "Diastolic Blood Pressure (mmHg)".

Table to include post-baseline visits of "Week 2", "Week 4", "Week 6", "Week 10", "3-Week Follow-up", "5-Week Follow-up", "Latest Follow-up".

Table 14.3.1.6.2: On-Drug Summary of Vital Signs (Safety Population Consenting to Protocol Version 3.0) (Page 1 of xx)

	Placebo	Serlopitant 5 mg
	(N=xxx)	(N=xxx)
<parameter> (<units>)</units></parameter>		
Baseline		
n	XX	XX
Mean	XX.X	XX.X
SD	XX.XX	XX.XX
Median	XX.X	XX.X
Min. to Max.	xx to xx	xx to xx
Week 2		
n	XX	XX
Mean	XX.X	XX.X
SD	XX.XX	XX.XX
Median	XX.X	XX.X
Min. to Max.	xx to xx	xx to xx
Absolute Change from Baseline		
n	XX	XX
Mean	XX.X	XX.X
SD	XX.XX	XX.XX
Median	XX.X	XX.X
Min. to Max.	xx to xx	xx to xx

Note: Baseline is the latest recorded value prior to first dose of study drug. Change calculated as post-baseline – baseline. SOURCE: USERNAME\SPONSOR\PROJECT\JOBNAME (DATE,TIME)

Table to include parameters in following order: "Temperature (degrees Celsius)", "Respiration Rate (breaths/min)", "Heart Rate (beats/min)", "Systolic Blood Pressure (mmHg)", "Diastolic Blood Pressure (mmHg)".

Table to include post-baseline visits of "Week 2", "Week 4", "Week 6", "Week 10".

Table 14.3.1.6.3: Post-Drug Summary of Vital Signs (Safety Population Consenting to Protocol Version 3.0) (Page 1 of xx)

	Placebo	Serlopitant 5 mg
_	(N=xxx)	(N=xxx)
<parameter> (<units>)</units></parameter>		
On-Drug Baseline		
n	XX	XX
Mean	XX.X	XX.X
SD	XX.XX	XX.XX
Median	XX.X	XX.X
Min. to Max.	xx to xx	xx to xx
3-Day Follow-up		
n	XX	XX
Mean	XX.X	XX.X
SD	XX.XX	XX.XX
Median	XX.X	XX.X
Min. to Max.	xx to xx	xx to xx
Absolute Change from On-Drug Baseline		
n	XX	XX
Mean	XX.X	XX.X
SD	XX.XX	XX.XX
Median	XX.X	XX.X
Min. to Max.	xx to xx	xx to xx

Note: On-Drug Baseline is the latest recorded value prior to last dose of study drug. Change calculated as post-baseline – baseline. SOURCE: USERNAME\SPONSOR\PROJECT\JOBNAME (DATE,TIME)

Table to include parameters in following order: "Temperature (degrees Celsius)", "Respiration Rate (breaths/min)", "Heart Rate (beats/min)", "Systolic Blood Pressure (mmHg)", "Diastolic Blood Pressure (mmHg)".

Table to include post-drug observation visits of "3-Day Follow-up", "1-Week Follow-up", "2-Week Follow-up", "3-Week Follow-up", "4-Week Follow-up", "5-Week Follow-up".

Table 14.3.1.7.1: Summary of Hospital Anxiety and Depression Scale (HADS)

(Safety Population)

(Page 1 of xx)

	Placebo	Serlopitant 5 mg
	(N=xxx)	(N=xxx)
<subscale></subscale>		
Baseline		
n	XX	XX
Mean	XX.X	XX.X
SD	XX.XX	XX.XX
Median	XX.X	XX.X
Min. to Max.	xx to xx	xx to xx
Week 4		
n	XX	XX
Mean	XX.X	XX.X
SD	XX.XX	XX.XX
Median	XX.X	XX.X
Min. to Max.	xx to xx	xx to xx
Absolute Change from Baseline		
n	XX	XX
Mean	XX.X	XX.X
SD	XX.XX	XX.XX
Median	XX.X	XX.X
Min. to Max.	xx to xx	xx to xx

Note: Baseline is the latest recorded value prior to first dose of study drug. Change calculated as post-baseline – baseline. "Latest Follow-up" visit includes the latest available follow-up information for each subject from the 3-Week, 4-Week or 5-Week Follow-up visits.

SOURCE: USERNAME\SPONSOR\PROJECT\JOBNAME (DATE,TIME)

Table to include subscales in following order: "Anxiety Subscale", "Depression Subscale".

Table to include post-baseline visits of "Week 4", "Week 10", "3-Week Follow-up", "5-Week Follow-up", "Latest Follow-up".

Table 14.3.1.7.2: On-Drug Summary of Hospital Anxiety and Depression Scale (HADS) (Safety Population Consenting to Protocol Version 3.0) (Page 1 of xx)

	Placebo	Serlopitant 5 mg
	(N=xxx)	(N=xxx)
<subscale></subscale>		
Baseline		
n	XX	XX
Mean	XX.X	XX.X
SD	XX.XX	XX.XX
Median	XX.X	XX.X
Min. to Max.	xx to xx	xx to xx
Week 4		
n	XX	XX
Mean	XX.X	XX.X
SD	XX.XX	XX.XX
Median	XX.X	XX.X
Min. to Max.	xx to xx	xx to xx
Absolute Change from Baseline		
n	XX	XX
Mean	XX.X	XX.X
SD	XX.XX	XX.XX
Median	XX.X	XX.X
Min. to Max.	xx to xx	xx to xx

Note: Baseline is the latest recorded value prior to first dose of study drug. Change calculated as post-baseline – baseline. SOURCE: USERNAME\SPONSOR\PROJECT\JOBNAME (DATE,TIME)

Table to include subscales in following order: "Anxiety Subscale", "Depression Subscale".

Table to include post-baseline visits of "Week 4", "Week 10"

Table 14.3.1.7.3: Post-Drug Summary of Hospital Anxiety and Depression Scale (HADS)
(Safety Population Consenting to Protocol Version 3.0)
(Page 1 of xx)

	Placebo	Serlopitant 5 mg
	(N=xxx)	(N=xxx)
<subscale></subscale>		
On-Drug Baseline		
n	XX	XX
Mean	XX.X	XX.X
SD	XX.XX	XX.XX
Median	XX.X	XX.X
Min. to Max.	xx to xx	xx to xx
3-Day Follow-up		
n	XX	XX
Mean	XX.X	XX.X
SD	XX.XX	XX.XX
Median	XX.X	XX.X
Min. to Max.	xx to xx	xx to xx
Absolute Change from On-Drug Baseline		
n	XX	XX
Mean	XX.X	XX.X
SD	XX.XX	XX.XX
Median	XX.X	XX.X
Min. to Max.	xx to xx	xx to xx

Note: On-Drug Baseline is the latest recorded value prior to last dose of study drug. Change calculated as post-baseline – baseline. SOURCE: USERNAME\SPONSOR\PROJECT\JOBNAME (DATE,TIME)

Table to include subscales in following order: "Anxiety Subscale", "Depression Subscale".

Table to include post-drug observation visits of "3-Day Follow-up", "1-Week Follow-up", "2-Week Follow-up", "3-Week Follow-up", "4-Week Follow-up", "5-Week Follow-up".

Table 14.3.1.8.1: Summary of Epworth Sleepiness Scale (ESS)
(Safety Population)
(Page 1 of xx)

	Placebo	Serlopitant 5 mg
700	(N=xxx)	(N=xxx)
ESS		
Baseline		
n	XX	XX
Mean	XX.X	XX.X
SD	XX.XX	XX.XX
Median	XX.X	XX.X
Min. to Max.	xx to xx	xx to xx
Week 4		
n	XX	XX
Mean	XX.X	XX.X
SD	XX.XX	XX.XX
Median	XX.X	XX.X
Min. to Max.	xx to xx	xx to xx
Absolute Change from Baseline		
n	XX	XX
Mean	XX.X	XX.X
SD	XX.XX	XX.XX
Median	XX.X	XX.X
Min. to Max.	xx to xx	xx to xx

Note: Baseline is the latest recorded value prior to first dose of study drug. Change calculated as post-baseline – baseline. "Latest Follow-up" visit includes the latest available follow-up information for each subject from the 3-Week, 4-Week or 5-Week Follow-up visits.

SOURCE: USERNAME\SPONSOR\PROJECT\JOBNAME (DATE,TIME)

Table to include post-baseline visits of "Week 4", "Week 10", "3-Week Follow-up", "5-Week Follow-up", "Latest Follow-up".

Table 14.3.1.8.2: On-Drug Summary of Epworth Sleepiness Scale (ESS) (Safety Population Consenting to Protocol Version 3.0) (Page 1 of xx)

	Placebo	Serlopitant 5 mg
	N=xxx	(N=xxx)
ESS		
Baseline		
n	XX	XX
Mean	XX.X	XX.X
SD	XX.XX	XX.XX
Median	XX.X	XX.X
Min. to Max.	xx to xx	xx to xx
Week 4		
n	XX	XX
Mean	XX.X	XX.X
SD	XX.XX	XX.XX
Median	XX.X	XX.X
Min. to Max.	xx to xx	xx to xx
Absolute Change from Baseline		
n	XX	XX
Mean	XX.X	XX.X
SD	XX.XX	XX.XX
Median	XX.X	XX.X
Min. to Max.	xx to xx	xx to xx

Note: Baseline is the latest recorded value prior to first dose of study drug. Change calculated as post-baseline – baseline. SOURCE: USERNAME\SPONSOR\PROJECT\JOBNAME (DATE,TIME)

Table to include post-baseline visits of "Week 4", "Week 10".

Table 14.3.1.8.3: Post-Drug Summary of Epworth Sleepiness Scale (ESS) (Safety Population Consenting to Protocol Version 3.0) (Page 1 of xx)

	Placebo	Serlopitant 5 mg
700	(N=xxx)	(N=xxx)
ESS		
On-Drug Baseline		
n	XX	XX
Mean	XX.X	XX.X
SD	XX.XX	XX.XX
Median	XX.X	XX.X
Min. to Max.	xx to xx	xx to xx
3-Day Follow-up		
n	XX	XX
Mean	XX.X	XX.X
SD	XX.XX	XX.XX
Median	XX.X	XX.X
Min. to Max.	xx to xx	xx to xx
Absolute Change from On-Drug Baseline		
n	XX	XX
Mean	XX.X	XX.X
SD	XX.XX	XX.XX
Median	XX.X	XX.X
Min. to Max.	xx to xx	xx to xx

Note: On-Drug Baseline is the latest recorded value prior to last dose of study drug. Change calculated as post-baseline – baseline. SOURCE: USERNAME\SPONSOR\PROJECT\JOBNAME (DATE,TIME)

Table to include post-drug observation visits of "3-Day Follow-up", "1-Week Follow-up", "2-Week Follow-up", "3-Week Follow-up", "4-Week Follow-up", "5-Week Follow-up".

Table 14.3.1.9: Summary of Pharmacokinetic Concentrations (Safety Population)

	Placebo	Serlopitant 5 mg
	(N=xxx)	N=xxx
<analyte> (<units>)</units></analyte>	, ,	, ,
Week 2		
n	XX	XX
Mean	XX.X	XX.X
SD	XX.XX	XX.XX
Median	XX.X	XX.X
Min. to Max.	xx to xx	xx to xx
Week 4		
n	XX	XX
Mean	XX.X	XX.X
SD	XX.XX	XX.XX
Median	XX.X	XX.X
Min. to Max.	xx to xx	xx to xx
Week 10		
n	XX	XX
Mean	XX.X	XX.X
SD	XX.XX	XX.XX
Median	XX.X	XX.X
Min. to Max.	xx to xx	xx to xx

Note: No imputation of missing values.

SOURCE: USERNAME\SPONSOR\PROJECT\JOBNAME (DATE,TIME)

Table to include analytes in following order: "M1/M1a", "M2/M2a", "M3", "Serlopitant".

Table 14.3.1.10: Summary of Menstrual Cycles (Safety Population)

	Placebo	Serlopitant 5 mg
	N=xxx	(N=xxx)
Number of Menstrual Cycles	,	
n	XX	XX
Mean	XX.X	XX.X
SD	XX.XX	XX.XX
Median	XX.X	XX.X
Min. to Max.	xx to xx	xx to xx
Duration of Menstrual Cycles		
n	XX	XX
Mean	XX.X	XX.X
SD	XX.XX	XX.XX
Median	XX.X	XX.X
Min. to Max.	xx to xx	xx to xx

Note: No imputation of missing values.

SOURCE: USERNAME\SPONSOR\PROJECT\JOBNAME (DATE,TIME)

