- Female subjects should be queried for presence of new breast masses or abnormal discharge, and abnormal vaginal bleeding or discharge
- Review menstrual diary and record dates of menstrual flow (if applicable)
- Obtain ECG
- Obtain vital signs
- Perform targeted physical examination, including weight
- Perform IGA PN-A
- Perform IGA PN-S

- Draw blood for clinical laboratory tests
 - Hematology
 - Chemistry
- Collect PK blood sample
- Assess and record any AEs and SAEs
- Review eDiary for compliance, re-train subject as needed
- Review study drug compliance with re-training as required
- Collect returned study drug
- Utilize IWRS to assign new bottle of study drug
- Confirm next scheduled visit date

6.5.7 *Week 4 Visit*

The Week 4 visit occurs 28 days (\pm 3 days) after the Baseline visit. At the Week 4 visit, the following procedures and assessments are to be performed:

- Ask the subject to complete the DLQI, HADS, and ESS questionnaires
- Assess and record any changes in the subject's concomitant medications
- Female subjects should be queried for presence of new breast masses or abnormal discharge, and abnormal vaginal bleeding or discharge
- Review menstrual diary and record dates of menstrual flow (if applicable)
- Obtain ECG
- Obtain vital signs
- Perform a urine pregnancy test for females of childbearing potential (with positive or equivocal results confirmed by a serum pregnancy test)
- Perform targeted physical examination, including weight
- Perform IGA PN-A
- Perform IGA PN-S
- Collect PK blood sample
- Assess and record any AEs and SAEs
- Collect returned study drug

- Utilize IWRS to assign new bottle of study drug
- Review eDiary for compliance, re-train subject as needed
- Review study drug compliance with re-training as required
- Confirm next scheduled visit date

6.5.8 *Week 6 Visit*

The Week 6 visit occurs 42 days (\pm 3 days) after the Baseline visit. At the Week 6 visit, the following procedures and assessments are to be performed:

- Assess and record any changes in the subject's concomitant medications
- Female subjects should be queried for presence of new breast masses or abnormal discharge, and abnormal vaginal bleeding or discharge
- Review menstrual diary and record dates of menstrual flow (if applicable)
- Obtain vital signs
- Perform a urine pregnancy test for females of childbearing potential (with positive or equivocal results confirmed by a serum pregnancy test)

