- Perform targeted physical examination, including weight
- Assess and record any AEs and SAEs
- Collect returned study drug
- Utilize IWRS to assign new bottle of study drug
- Review eDiary for compliance, re-train subject as needed
- Confirm next scheduled visit

6.5.9 *Week 10 Visit*

The Week 10 visit occurs 70 days (\pm 7 days) after the Baseline visit. At the Week 10 visit, the following procedures and assessments are to be performed:

- Ask the subject to complete the DLQI, HADS, and ESS questionnaires
- Assess and record any changes in the subject's concomitant medications
- Female subjects should be queried for presence of new breast masses or abnormal discharge, and abnormal vaginal bleeding or discharge
- Review menstrual diary and record dates of menstrual flow (if applicable)

- Obtain ECG
- Obtain vital signs
- Perform targeted physical examination, including weight
- Perform IGA PN-A
- Perform IGA PN-S
- Perform a urine pregnancy test for females of childbearing potential (with positive or equivocal results confirmed by a serum pregnancy test)
- Draw blood for clinical laboratory tests (morning blood sampling due to Endocrine assessments)
 - Reproductive endocrine labs for females under 55 years of age at consent
 - Endocrine
 - Hematology
 - Chemistry
- Collect PK blood sample
- Assess and record any AEs and SAEs
- Collect returned study drug
- Obtain photos (at selected sites, only subjects that signed photography consent)
- Review eDiary for compliance, inform subject to continue entering WI-NRS score until Follow-up visit
- Review study drug compliance with re-training as required
- Confirm next scheduled visit date

6.5.10 ***Post-Drug Observation Visits***

There are five (5) post-drug observation visits, and a Follow-up visit to complete the post-observation period.

The Post-Drug Observation Visits occur 3 days (± 1 days), 7 days (± 3 days), 14 days (± 3 days), 21 days (± 3 days), and 28 days (± 3 days) after the Week 10 Visit.

At the Post-Drug Observation Visits, the following procedures and assessments are to be performed:

- Ask the subject to complete the HADS and ESS questionnaires
- Assess and record any changes in the subject's concomitant medications
- Female subjects should be queried for presence of new breast masses or abnormal discharge, and abnormal vaginal bleeding or discharge
- Review menstrual diary and record dates of menstrual flow (if applicable)
- Obtain vital signs
- Assess and record any AEs and SAEs

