In order to assess physical dependence and withdrawal, data collected during a 5-week post-drug observation period will be summarized. For each assessment, an on-drug baseline value is defined as Week 10 (for subjects completing treatment) or the last observation prior to last dose of study drug (for subjects that discontinued treatment early).

The observed data and change from on-drug baseline for the HADS will be summarized with descriptive statistics by time point (Day 3, Day 7, Weeks 2, 3, 4 and 5 post last dose of study drug). Both the Depression and the Anxiety subscales will be reported.

The observed data and change from on-drug baseline for the ESS will be summarized with descriptive statistics by time point (Day 3, Day 7, Weeks 2, 3, 4 and 5 post last dose of study drug).

Vital signs including change from on-drug baseline will be summarized with descriptive statistics for each post-study drug observation visit.

Overall ECG assessments (abnormal or normal), as well as observed and change from on-drug baseline for ECG parameters, will be summarized for the 5-week post-study drug visit. In addition, a summary of how many subjects developed a post-drug abnormal result will be presented.

Assessment of AEs reported after study drug discontinuation, i.e. during the post-study drug observation period, will be summarized separately by treatment group.

8.11 **Interim Analyses**

No interim analysis is planned.

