### 6.9 Safety Evaluation

### **6.9.1** Extent of Exposure

The extent of exposure to study drug in each treatment group will be summarized by days with exposure and total number of tablets used.

A subject will be considered compliant with the dosing regimen if the subject takes 80% to 120% of the expected number of doses while enrolled in the study. Total number of days of exposure will be computed as follows:

```
Total Exposure = Date of Last Dose – Date of First Dose + 1

Total Doses = (Date of Last Dose – Date of First Dose + 1 + 2)

– Missed Doses + Extra Doses
```

Treatment compliance will be based on the expected number of doses given the treatment period duration. The number of expected doses will be computed from the Baseline/Day 1 visit date and the Week 10 visit date. If a subject does not have a Week 10 visit, the number of expected doses will be calculated based on end of treatment period date given available information (e.g., date of last dose, last completed visit date).

```
Expected Doses = End of Treatment Period Date – Day 1 Date + 2
```

If the subject is documented as dosing on the End of Treatment Period Date, a dose will be added to the Expected Doses. To allow for the +7 day window around Week 10 that is used for defining PP population, if the number of expected doses exceeds 80, the number of expected doses will be considered 80 doses.

Percent compliance will be calculated from total number of doses and total number of expected doses as follows:

```
Percent Compliance = 100*(Total Doses/Expected Doses).
```

Percent compliance will not be calculated for subjects who are lost to follow-up during the treatment period.

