### 6.9.4.7 Potential for Physical Dependence

In order to assess physical dependence and withdrawal, data collected during a 5-week post-drug observation period will be summarized. For each assessment, an on-drug baseline value is defined as Week 10 (for subjects completing treatment) or the last observation prior to last dose of study drug (for subjects that discontinued treatment early).

The observed data and change from on-drug baseline for the HADS will be summarized with descriptive statistics by time point (3-Day Follow-up, and 1-, 2-, 3-, 4- and 5-Week Follow-up). Both the Depression and the Anxiety subscales will be reported.

The observed data and change from on-drug baseline for the ESS will be summarized with descriptive statistics by time point (3-Day Follow-up, and 1-, 2-, 3-, 4- and 5-Week Follow-up).

Vital signs including change from on-drug baseline will be summarized with descriptive statistics for each post-study drug observation visit.

Overall ECG assessments (abnormal or normal), as well as observed and change from on-drug baseline for ECG parameters, will be summarized for the 5-week post-study drug visit. In addition, a summary of how many subjects developed a post-drug abnormal result will be presented.

Assessment of AEs reported after study drug discontinuation, i.e. during the post-study drug observation period, will be summarized separately by treatment group. AEs during the post-study drug observation period will be summarized by weekly periods and sex.

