	Dose L: Date of Last Dose F: xxxx-xx-xx	D: Date of Study Discontinuation (Day) 1  F: Date of First T: Primary Reason for Treatment Dose Discontinuation  L: Date of Last Dose Discontinuation  F: xxxx-xx-xx D: xxxx-xx-xx (xx)	D: Date of Study Discontinuation (Day) 1  F: Date of First T: Primary Reason for Treatment Dose Discontinuation S: Grade 2  L: Date of Last S: Primary Reason for Study R: Relationship to Dose Discontinuation Study Treatment  F: xxxx-xx-xx D: xxxx-xx-xx (xx) A: xxxxxxxx

Listing sorted by Subject, Start Date, End Date, and Adverse Event.

Day is calculated as date - date of first dose for dates prior to first dose. Otherwise, day is calculated as date - date of first dose + 1 for dates on or after first dose.

 Grade 1 = Mild; Grade 2 = Moderate; Grade 3 = Severe; Grade 4 = Life Threatening; Grade 5 = Death.
Note: ITT = Intent-to-Treat Population; S = Safety Population; PP = Per-Protocol Population.
SOURCE: USERNAME\SPONSOR\PROJECT\JOBNAME (DATE, TIME)

Listing 16.2.7.2.1: Hospital Anxiety and Depression Scale

Treatment Group

(Page xx of yy)

V: Visit

Subject Age/Sex Evaluable D: Date of Assessment (Day) 1 Question Result XXXXXXXX XXXX xxxxxxx V: xxxxxxxxx I feel tense or 'wound up' xxxxxxxxxxxxxxxx I still enjoy the things I used to enjoy D: xxxx-xx-xx (xx) xxxxxxxxxxxxxxxx I get a sort of frightened feeling as if something awful is about to happen xxxxxxxxxxxxxxxxx I can laugh and see the funny side of things xxxxxxxxxxxxxx Worrying thoughts go through my mind XXXXXXXXXXXXXXXXXX I feel cheerful XXXXXXXXXXXXXXXXXX I can sit at ease and feel relaxed xxxxxxxxxxxxxxxx Depression Subscale

Anxiety Subscale

Day is calculated as date - date of first dose for dates prior to first dose. Otherwise, day is calculated as date - date of first dose + 1 for dates on or after first dose.

Note: ITT = Intent-to-Treat Population; S = Safety Population; PP = Per-Protocol Population.

SOURCE: USERNAME\SPONSOR\PROJECT\JOBNAME (DATE, TIME)

Listing 16.2.7.2.2: Epworth Sleepiness Scale
Treatment Group
(Page xx of yy)

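### Six SAP table shells omit the Week 10 rule for the on-drug baseline, so a completer whose last dose precedes the Week 10 visit could be measured from Week 4 or Week 6

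*SAP*

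**What the plan says.** SAP 6.9.4.7 gives a two-part definition covering HADS, ESS, vital signs and ECG. For those who finish treatment, "an on-drug baseline value is defined as Week 10 (for subjects completing treatment"). For those who stop early, the baseline is "the last observation prior to last dose of study drug (for subjects that discontinued treatment early"). Protocol 8.10.9 gives the same definition.

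The shells in SAP section 10 say something else. Beneath each table that uses this baseline the note reads "On-Drug Baseline is the latest recorded value prior to last dose of study drug", with no separate rule for completers. The tables are 14.3.1.5.2.1, 14.3.1.5.2.2 and 14.3.1.5.2.3 (ECG), 14.3.1.6.3 (vital signs), 14.3.1.7.3 (HADS) and 14.3.1.8.3 (ESS).

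Neither document says whether body text or shell note governs. SAP section 8 declares no departures from the planned analyses, so the note is not a declared change of definition.

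**The concern.** Whether the drug causes physical dependence is a stated safety objective (Protocol section 2, SAP section 3). Protocol 6.2.7 notes that this drug class has no withdrawal instrument of its own, so the objective leans on HADS, ESS, vital signs, ECG and post-drug adverse events. For the first four, the natural reading is the change after stopping drug, measured from the end of treatment.

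The shell note can move the starting point back into the treatment period for some completers. Their post-drug rows would then contain both what happened after stopping and what happened during the last weeks on drug. Improvement on treatment could offset a real rebound, and worsening on treatment could resemble one. In the ECG shift table, an abnormality first seen at Week 10 and still present at follow-up could be counted as a post-drug shift.

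**Working it through.** **1. Which tables.** Six shells use an on-drug baseline and all six carry the note. The post-drug adverse event shells (14.3.1.2.x) use no baseline value and are unaffected.

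**2. For whom the rules differ.** For early discontinuers the text and the note agree. They can differ only for completers, and only when the Week 10 assessment does not count as being before the last dose.

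**3. Can a completer's last dose precede the Week 10 visit date?** SAP 6.9.1 calculates expected doses as end-of-treatment date minus Day 1 date plus 2. With 3 tablets on Day 1 and one a day up to study day L, tablets = 3 + (L − 1), so L = expected doses − 2.

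| Week 10 visit, days after Baseline | Visit study day | Expected doses | Implied last dose day L | Visit day − L |
|---|---|---|---|---|
| 63 | 64 | 65 | 63 | 1 |
| 70 | 71 | 72 | 70 | 1 |
| 77 | 78 | 79 | 77 | 1 |

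The default count therefore ends the day before the visit. A visit-day dose is handled as an exception: "If the subject is documented as dosing on the End of Treatment Period Date, a dose will be added to the Expected Doses". For the nominal visit that gives 72 + 1 = 73. Protocol 6.5.9 lists no dosing step at Week 10 and includes "Collect returned study drug". A last dose on the day before the visit is thus an ordinary case.

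**4. Where the note sends such a completer.** Under Protocol Appendix A, Table 2, HADS and ESS are collected on treatment only at Weeks 4 and 10, post-dose ECGs at Weeks 2, 4 and 10, and vital signs at Weeks 2, 4, 6 and 10. Without Week 10, the latest scheduled value is Week 4 for HADS, ESS and ECG, and Week 6 for vital signs. Visits fall 28 ± 3 days (Week 4), 42 ± 3 days (Week 6) and 70 ± 7 days (Week 10) after Baseline.

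- Week 4 to Week 10: 70 − 28 = 42 days; minimum 63 − 31 = 32; maximum 77 − 25 = 52.
- Week 6 to Week 10: 70 − 42 = 28 days; minimum 63 − 45 = 18; maximum 77 − 39 = 38.

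**5. Effect on the change rows.** For an affected completer with a Week 4 baseline:

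post-drug value − Week 4 = (post-drug value − Week 10) + (Week 10 − Week 4).

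The first bracket is the quantity defined in 6.9.4.7; the second is on-treatment change. A row mean moves by the share of subjects affected times their mean Week 4 to Week 10 change. The documents give neither factor, so no size in scale points can be stated.

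**6. Completers who dosed on the visit day.** The study-baseline note in Tables 14.3.1.7.1 and 14.3.1.8.1 takes the latest value before the first dose. HADS and ESS are first collected at the Baseline visit, on the same date as the loading dose (Protocol 6.5.4). A strict date comparison would leave every subject without a HADS or ESS baseline, so same-date values must be accepted there. The same convention applied to the last dose probably keeps Week 10 for visit-day dosers.

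**The case against.** The best reply is that two matching definitions in the body text outweigh an abbreviated footnote, and that a careful programmer would follow the text. That is plausible, but it leaves six tables whose notes misdescribe their baseline. Nothing in the documents rules out programming from the shells.

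Second, the dose formula in SAP 6.9.1 is a compliance denominator and does not define the last dose. Protocol Table 3 has dosing recorded daily through the Week 10 visit, and the supply of 5 × 18 = 90 tablets covers a visit-day dose. This stands. It means the number affected is unknown and may be small; it does not remove completers whose last dose came before the visit.

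Third, a rebound would not be invisible. Tables 14.3.1.6.3, 14.3.1.7.3 and 14.3.1.8.3 show observed post-drug values, and the paired on-drug Tables 14.3.1.6.2, 14.3.1.7.2 and 14.3.1.8.2 show observed Week 10 values in the same subset. This stands for vital signs, HADS and ESS. ECG has no such paired table: its Week 10 summaries cover the whole Safety Population.

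Fourth, the shift can arise in both arms, so the comparison with placebo is distorted only if the arms differ in the share affected or in on-treatment change. This also stands.

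A reader might infer that visit-day dosers lose Week 10 as well, because the HADS and ESS listings show a date without a time. The documents do not support that: the study-baseline convention must already accept same-date values, and a listing layout does not show that times were not collected.

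**Conclusion.** The inconsistency is real and should be corrected. In six of six shells the note omits the completers' Week 10 rule in SAP 6.9.4.7 and Protocol 8.10.9. If the note is programmed, a completer whose last dose was before the Week 10 visit date has a baseline 42 days too early for HADS, ESS and ECG (32 to 52), or 28 days too early for vital signs (18 to 38). This assumes that the earlier scheduled value was recorded and that no unscheduled value lies in between.

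The consequence is limited. It arises only if the note is followed instead of the text. The tables are untested descriptive summaries restricted to subjects who consented to Protocol Version 3.0. Efficacy and post-drug adverse event tables are untouched.

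A reader might go further and infer that a rebound of a given number of points would be hidden, or that the dependence assessment fails. Neither follows: the plan supplies no figure for the share affected or for on-treatment change, and for three of the four measures the Week 10 and post-drug values remain on display.

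**What to change.** Before unblinding, replace the note in the six shells with the SAP 6.9.4.7 rule: the on-drug baseline is the Week 10 value for a subject who completed treatment, and the last value before the final dose for a subject who stopped early.

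At dry run, confirm on subject-level data that every completer's on-drug baseline equals that subject's Week 10 value for HADS, ESS, vital signs and ECG. The summary tables alone cannot show this.

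The cost is one wording edit repeated in six notes and one programming check. It needs no protocol amendment, no new data and no change to 6.9.4.7.
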